8.1 Reporting of Adverse Events

The AE reporting requirements for this study are as follows:

- All AEs that meet the definition of serious and occur within the perioperative period (intraoperative to hospital discharge)
- All AEs related to the operative site, regardless of seriousness or time of occurrence

On postoperative functional evaluations, investigators and SCs will be prompted to question subjects as to whether they have seen a doctor for any reason, been hospitalized for any reason or have a current impediment to their function.

Additionally, SCs will be responsible for following up with the subjects regarding any questionable responses received on the Follow-up Questionnaire administered in postoperative years 6

through 10. If it is determined upon this further investigation that a protocol-defined AE has occurred, the SC will be responsible for completing an AE eCRF, submitting the event to Stryker and reporting to the IRB/EC, as required.

The following decision tree facilitates identification of AEs for which reporting is required under this study protocol:

[figure not shown]

Figure 4. Adverse Event Decision Tree

General Physical Examination Findings

At screening for inclusion into the study, any clinically significant abnormality should be recorded as a preexisting condition and reported on the Demographics eCRF. From the time of consent forward, any new clinically significant findings or abnormalities that meet the definition of a protocol defined AE must also be recorded and documented as an AE.

Adverse Event Reporting Period

The study period during which AEs must be reported is normally defined as the period from the initiation of any study procedures to the end of the study treatment follow-up. The start of study procedures is considered to be the point of consent. Any AEs which fit the protocol defined reportable events must be reported from the time of consent until study completion.

At each contact with the subject the investigator must seek information on AEs by specific questioning and, as appropriate, by examination. Information on protocol defined AEs should be recorded immediately in the source document and also in the appropriate AE module of the eCRF. All clearly related signs, symptoms and abnormal diagnostic procedure results should be recorded in the source document and grouped under one diagnosis, as appropriate. The clinical course of each event should be followed until resolution or until it is determined at the end of the study that the AE will not resolve.

8.2 General Adverse Event Definitions

Following is a list of general AE definitions. For the purposes of this study, only SAEs, excluding elective procedures, as well as all AEs related to the operative site should be reported.

Adverse Event

An **AE** is any untoward medical occurrence in a clinical investigation subject, which changes the medical baseline of the subject. An AE can be an unfavorable and unintended sign, symptom or disease, whether or not related to the study device (AEs may also be referred to as complications). See Section 8.1, Reporting of Adverse Events, for the AE reporting requirements for this study.

Anticipated Adverse Event

An **anticipated AE** is an AE, of which the nature, severity or degree of incidence is known and identified in applicable product labeling, published literature or the study protocol. The list of anticipated events is provided in Section 12, Risk/Benefit Assessment.

Serious Adverse Event

A **SAE** meets one or more of the following definitions:

- Resulted in in-patient hospitalization
- Resulted in prolonged existing hospitalization
- Resulted in persistent or significant disability/incapacity
- Resulted in permanent impairment of a body function or permanent damage to a body structure
- Necessitated medical or surgical intervention to preclude permanent impairment of a body function or permanent damage to a body structure
- Was a life-threatening situation
- Resulted in patient death

Adverse Device Effect

An **adverse device effect** (ADE) is a negative change in the subject's health that may have been caused by, or associated with, the use of the device.

Unanticipated Adverse Device Effect

An **unanticipated adverse device effect** (UADE) is any serious adverse effect on health, safety or any life-threatening problem or death caused by, or associated with, a device if that effect is a problem or death not previously identified in nature, severity or degree of incidence, or any other unanticipated serious problem associated with a device and related to the rights, safety or welfare of subjects.

8.3 Study Sponsor Notification by Investigator

Of reportable AEs, certain events must be submitted to Stryker within 24 hours for timely notification:

Adverse events that require time sensitive reporting:

An adverse event should be reported to Stryker Clinical Research either by telephone/fax/email within 24 hours of the site becoming aware of the event if any of the following apply:

- The AE is considered by the investigator to be device related or if the investigator is uncertain regarding the device related assessment;
- The AE required a reoperation of the study hip or a revision of any study hip components.

An AE eCRF must be completed within 24 hours. If a SAE occurs, the de-identified source documentation must be uploaded to the appropriate location within Stryker's Electronic Data Capture (EDC) system within 24 hours of the investigative center's SAE awareness. See Section 11, Data Management, for additional details of Stryker's EDC system. These reports will be evaluated by Stryker to determine if a PER is required.

It is recommended that all other reportable AEs are submitted through eCRF entry within 2 weeks.

At the time of the initial report, the following information should be provided:

Subject number	Whether study treatment was
A description of the event	discontinued
Date of onset	Investigator assessment of the
Current status	association between the event and
	the study treatment
	,

8.3.1 Ethics Committee/Institutional Review Board Notification by Investigator

Reports of AEs (including follow-up information) must be submitted to the EC or IRB according to their specific requirements. Copies of each report and documentation of EC/IRB notification and receipt will be kept with the investigator's study files.

8.4 Recording of Adverse Events

All protocol defined AEs occurring during the study period must be recorded; this includes events that occur between visit intervals. The clinical course of each event should be followed until resolution or stabilization.

8.5 Medical Monitoring

It is the responsibility of the investigator to oversee the safety of the study at his/her center. This safety monitoring will include careful assessment and appropriate reporting of AEs, as previously noted. Stryker will conduct formal investigations via the Product Surveillance Department of those AEs which are submitted through our PER System.

9 Statistical Plan

9.1 Efficacy

9.1.1 Primary Efficacy Parameters

The primary efficacy parameter is the success rate at 5 years postoperative with the Secur-Fit Advanced Hip Stem, where success is defined as absence of femoral stem revision and/or removal for aseptic loosening or device-related femoral fracture at 5 years postoperative.

9.1.2 Secondary Efficacy Parameters

The secondary efficacy parameters include:

- The all-cause revision and/or removal rates of the Secur-Fit Advanced Hip Stem;
- The rate of device-related femoral fracture among patients implanted with the Secur-Fit Advanced Hip Stem within 30 days postoperative; and
- The component exposure or countersink upon final seating intraoperative.

Additional data will be collected as noted in Section 2.1.3; related details are in Section 9.4.1 Data Summary.

9.1.3 Primary Efficacy Analysis

The primary hypothesis to be tested will be that the success rate at 5 years postoperative with the Secur-Fit Advanced Hip Stem is not worse than 99% with a non-inferiority margin of 2.5%.

That is, the following hypothesis will be tested:

Ho: Pt <= 99% - 2.5% HA: Pt > 99% - 2.5%

Here, Pt is the success rate at 5 years postoperative with the Secur-Fit Advanced Hip Stem

A 90% two-sided confidence interval will be computed for the success rate at 5 years. If the lower bound of the confidence interval is greater than 96.5%, then the non-inferiority hypothesis will be supported.

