9.4 Statistical Methodology

9.4.1 Data Summary

Descriptive statistics will be computed for all baseline conditions and demographic parameters. That is, for continuous data, the N, mean, median, standard deviation, minimum and maximum will be computed. For categorical data, the frequency will be computed. The data will be presented by appropriate subgroups (e.g., center, gender).

A Kaplan-Meier survivorship curve will be displayed for revision and/or removal of the Secur-Fit Advanced Hip Stem for aseptic loosening or device-related femoral fracture.

A Kaplan-Meier survivorship curve will be displayed for all-cause revision and/or removal of the Secur-Fit Advanced Hip Stem.

For the additional data collected according to Section 2.1.3, data will be summarized according to visit. For parameters represented by continuous variables (e.g., ROM), the

summaries will consist of the N, mean, median, standard deviation, minimum, and maximum values. For categorical variables (e.g., Mobility from EQ-5D), the frequency and percentage in each category will be presented. A paired t-test will be performed to evaluate the change in clinical and patient outcomes, preoperative to 5 years within the Secur-Fit Advanced Hip Stem. The 1-year, 2-year and 5-year SF-12, LEAS and HHS will be presented with respect to improvement from preoperative scores.

For the Follow-up Questionnaire, frequency and percentage will be computed for each category according to visits. Applicable lists based on Follow-up Questionnaire will be generated to capture AEs.

For radiographic data, data will be presented according to visits for available parameters. Frequency and percentage will be computed for radiolucency according to visit. Lists will be generated for migration over time. Radiographic failure will be evaluated, where radiographic failure is defined as subsidence of greater than 5 mm, migration of greater than 5° in any direction or at least 2 mm radiolucency in all zones within a single view.

Documentation of statistical analyses utilizing SAS® software version 9.1.3 or higher.

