9.4.2 Sample Size Justification

With a reference value of 99% of success rate at 5 years, under the regular assumptions of 5% significance level (or 95% one-sided confidence interval), 80% power, 2.5% non-inferiority margin, the sample size is 277. After factoring a 15% lost to follow-up rate, the final sample size is 326. A significant decrease in screening/enrollment occurred after 2018, resulting in a final sample size of 314 cases.

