9.4.4 Analysis Population

Per Protocol Population: The study population for analysis will include all non-censored subjects who receive the Secur-Fit Advanced Hip Stem and are available for efficacy evaluation.

The primary and secondary efficacy analyses will be based on the per protocol population.

Safety Population: The safety population will include all non-censored subjects who received the Secur-Fit Advanced Hip Stem.

The safety analysis will be based on the safety population.

10 Study Procedures

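### The deciding 90% interval has no stated construction, and 5 failures in 267 pass or fail depending on it; separately, 314 cases at the plan's 15% loss leave 267, not the 277 tied to 80% power

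*Combined protocol and SAP*

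**What the plan says.** Section 9.1.3 sets the hypotheses as "Ho: Pt <= 99% - 2.5% HA: Pt > 99% - 2.5"%, so the null success rate is 96.5%. The test rests on one interval: "A 90% two-sided confidence interval will be computed for the success rate at 5 years". The decision rule is "If the lower bound of the confidence interval is greater than 96.5%, then the non-inferiority hypothesis will be supported". The level and the threshold are given; the method of construction is not, and Sections 9.4.1, 9.4.2 and 9.4.4 do not supply it.

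The type of estimate is also left open. Section 9.4.4 restricts the efficacy analysis to "all non-censored subjects who receive the Secur-Fit Advanced Hip Stem and are available for efficacy evaluation", which reads like a simple proportion. Section 9.4.1 plans a survival curve for the same endpoint: "A Kaplan-Meier survivorship curve will be displayed for revision and/or removal". It does not link that curve to the deciding interval.

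On sample size, Section 9.4.2 takes a 99% reference rate and says "under the regular assumptions of 5% significance level (or 95% one-sided confidence interval), 80% power, 2.5% non-inferiority margin, the sample size is 277". It continues "After factoring a 15% lost to follow-up rate, the final sample size is 326" and closes with "A significant decrease in screening/enrollment occurred after 2018, resulting in a final sample size of 314 cases". No evaluable number or power is given for 314.

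**The concern.** When the expected success rate is 99% and only a handful of failures will be seen, the usual intervals for a proportion differ by more than half a percentage point at the lower end. That is large against a 2.5-point margin. Leaving the method open therefore leaves open how many failures the device may have and still be declared non-inferior.

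Two things are at stake. First, whether the rule keeps the stated 5% level depends on the unstated choice. Second, the study is open-label with a single arm, so failures are visible as they accrue. A method fixed only at the analysis could be chosen, or appear to have been chosen, with the count known.

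The sample-size point is separate and smaller. The reader is told what 277 cases deliver and then that 314 were enrolled, but not what 314 deliver.

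**Working it through.** **Inputs.** Null rate 96.5%, two-sided 90% interval, threshold 96.5% (Section 9.1.3). Reference rate 99%, one-sided 5%, power 80%, margin 2.5%, 277 before loss, 15% loss, 326, then 314 (Section 9.4.2). z(0.95) = 1.645, z(0.80) = 0.8416.

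**1. Reproducing the plan's figures.** The formula behind 277 is not named. The one-sample normal formula with null variance gives

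n0 = [(1.645·√(0.965·0.035) + 0.8416·√(0.99·0.01)) / 0.025]² = [(0.3023 + 0.0837)/0.025]² = 238.4.

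With the continuity correction, n = (n0/4)·[1 + √(1 + 2/(n0·0.025))]² = 276.99, so 277. Then 277/0.85 = 325.9, so 326. Both figures reproduce. A formula with Wald variance gives (1.645 + 0.8416)²·0.99·0.01/0.025² = 97.9, or 135.0 corrected. The match therefore points away from Wald, but it does not define the analysis interval.

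**2. What 314 leaves.** 314 × 0.85 = 266.9, about 267, which is 10 below 277. Keeping 277 requires loss of at most 1 − 277/314 = 11.8%.

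**3. Lower 90% limits with 5 failures.** For Wald at 267: p = 262/267 = 0.98127, and 0.98127 − 1.645·√(0.98127·0.01873/267) = 0.9676.

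| Method | 5 of 267 | 5 of 277 |
|---|---|---|
| Wald | 96.76% pass | 96.88% pass |
| Wilson | 96.20% fail | 96.34% fail |
| Clopper-Pearson | 96.10% fail | 96.24% fail |

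At 267, Wald fails at 6 failures (96.26%); Wilson (96.70%) and Clopper-Pearson (96.60%) pass at 4. So Wald allows 5 failures and the other two allow 4.

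**4. Kaplan-Meier reading.** With no censored cases, 5 failures in 267 give 96.76% by the untransformed Greenwood limit (identical to Wald, pass) and 96.13% by log-log (fail). Choosing Kaplan-Meier does not remove the ambiguity.

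**5. Exact error rate and power.** X is the number of failures.

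| Evaluable n | Failures allowed | Type I error, P(X ≤ c) at 3.5% failures | Power, P(X ≤ c) at 1% failures |
|---|---|---|---|
| 267 | 5 (Wald) | 9.2% | 94.7% |
| 267 | 4 (Wilson, Clopper-Pearson) | 4.2% | 86.8% |
| 277 | 5 (Wald) | 7.6% | 93.8% |
| 277 | 4 (Wilson, Clopper-Pearson) | 3.3% | 85.3% |

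Over 251 to 314 evaluable cases (20% to 0% loss of 314), type I error is:
- Wald: 6.5% to 12.5%, above 5% at every size.
- Wilson: 2.3% to 5.8%, above 5% at 252–258 and 290–297.
- Clopper-Pearson: 1.9% to 5.0%, never above 5%.

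**6. How likely the disputed count is.** P(X = 5 | n = 267) is 7.8% if the true rate is 99%, and 17.5% if it is 98% (an assumed value for illustration).

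**7. Power by the plan's likely formula.** At 267 the continuity-corrected formula gives 77.6% (80.0% at 277). Without the correction it gives 85.7% at 267.

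**The case against.** The strongest reply is that the sample-size point has no consequence under the proposed method. Clopper-Pearson allows 4 failures at both 267 and 277, and exact power is slightly higher at 267 (86.8% against 85.3%). The 15% is also a planning figure, and actual loss may be below 11.8%. This stands: the second point is a missing restatement, not evidence of an underpowered study.

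It can also be said that nothing in the plan proposes Wald, that the formula matching 277 points away from it, and that among the three methods compared at 267 the verdict differs at only one count. All true. But that count is the pass/fail boundary, and the text does not exclude Wald. Other candidates widen the disagreement. The score interval with continuity correction, the natural partner of the formula that gives 277, has a lower limit of 96.45% at 4 of 267 (fail) and 96.58% at 4 of 277 (pass). Under it only 3 failures pass at 267, with exact power 72.1%. The favourable 86.8% therefore depends on the method named.

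Two further points are fair. Clopper-Pearson is a preference, since Wilson also holds 5% at both 267 and 277. And Section 9.4.4 leans clearly towards a proportion, with the Kaplan-Meier curve only for display. That is why the sponsor is asked to confirm this reading.

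**Conclusion.** The concern holds on both points.

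The first is the more important. The primary decision rule is incomplete, and a reading that the text permits gives a type I error of 9.2% at 267 against the stated 5%. The permitted number of failures at 267 is 5 or 4 depending on whether Wald or one of Wilson and Clopper-Pearson is used.

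The second is a gap in the justification. At the plan's own loss rate, 314 enrolled give 267 evaluable, not 277, and no power is stated for the new number. Whether power is below 80% depends on the method: 86.8% by exact Clopper-Pearson, 77.6% by the continuity-corrected formula that appears to lie behind 277.

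These figures assume a binomial proportion among evaluable cases, the 15% loss applied to 314, and true rates of 96.5% (null) and 99% (reference). The point should be dealt with before the 5-year analysis; it does not call the margin or the threshold into question.

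**What to change.** In Section 9.1.3, name the interval: a two-sided 90% Clopper-Pearson interval for the binomial proportion of successes among evaluable per-protocol cases, with the Kaplan-Meier curve descriptive. The sponsor should confirm that a proportion is intended. Of the three methods compared, Clopper-Pearson is the only one that stays within 5% at every size from 251 to 314.

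In Section 9.4.2, after the sentence on 314, add that:
- with 15% loss about 267 cases are expected to be evaluable, fewer than 277;
- under the Clopper-Pearson rule, at most 4 failures in 267 support non-inferiority, with type I error 4.2% at a true rate of 96.5% and power 86.8% at 99%;
- the allowed number of failures and the power move in steps and will be recalculated at the actual evaluable number.

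The 77.6% should be quoted only if the sponsor confirms that the continuity-corrected formula was used.

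The cost is one phrase and three sentences, with no new data or patients. The downside is some conservatism. Clopper-Pearson allows 4 failures from 259 to 297 evaluable cases but only 3 from 220 to 258, so power at 99% falls from 88.0% at 259 to 74.1% at 258 (a loss of 1 − 258/314 = 17.8%).

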9.1.4 Secondary Efficacy Analysis

The all-cause revision and/or removal rates of the Secur-Fit Advanced Hip Stem will be reported.

The rate of device-related femoral fracture among patients implanted with the Secur-Fit Advanced Hip Stem within 30 days postoperative will be evaluated.

The mean amount of unintended exposure or countersink of the femoral component upon final seating will be presented; standard deviation, median, minimum, and maximum will be displayed.

The analysis for the additional data collection is in 9.4.1 Data Summary.

9.2 Safety

9.2.1 Safety Parameters

Safety parameters include all protocol-defined adverse events as well as revision and/or removal rates. For details regarding protocol-defined adverse events, see Section 8.1.

9.2.2 Safety Analyses

The frequency and percentage of all protocol-defined adverse events will be tabulated. For details regarding protocol-defined adverse events, see Section 8.1.

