2.2 Safety

All operative site events occurring at any time as well as all serious adverse events (SAEs) occurring in the perioperative period (intraoperative to hospital discharge) will be collected and compared to published data. It is expected that the AE rates reported for the Secur-Fit Advanced Hip Stem will be comparable to those reported in the literature for other primary femoral stems on the market. Details regarding AE definitions, recording and reporting are in Section 8 of this protocol, Adverse Events.

3 Clinical Study Plan

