3.4 Estimated Study Duration

The enrollment period is estimated to be a maximum of 24 months; cases will be evaluated as per the evaluation schedule until each case reaches 10 years.

To allow for a learning curve with the use of the device, enrollment of cases into the study will commence when three cases have been completed at the center using the Secur-Fit Advanced Hip Stem.

4 Eligibility

The following criteria will be used to distinguish patients eligible for enrollment into this study. Proper implant selection must consider design, fixation, and environmental variables including: patient weight, age, bone quality and size, activity level and pre-operative level of health, as well as the surgeon's experience and familiarity with the device.

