10.3 Early Withdrawal of Subjects

When and How to Withdraw Subjects

In the event that the subject is discontinued by the investigative center prior to the final study evaluation, the subject will be notified by the center that he/she is no longer in the study and a Study Termination eCRF will be completed.

The following is a list of reasons for which subjects may be withdrawn and the date of termination that should be used on the Study Termination eCRF in each situation. This list is not all inclusive:

Termination Reason	Date of Termination
Death	Date of death
Investigative center termination	Date of study close-out visit
Lost to follow-up	Date Stryker termination approval given
Voluntary withdrawal	Date subject notified center of withdrawal
Revision/removal of study device	Date of revision/removal procedure
Study device not implanted	Date of surgery
Surgery not performed	Date Stryker termination approval given

At the time of study surgery it is required that the following components are implanted for each treatment group:

Secur-Fit Advanced Hip Stem with any compatible Stryker acetabular components:

- o Secur-Fit Advanced Hip Stem
- Compatible Stryker femoral head
- o Compatible Stryker acetabular insert
- Compatible Stryker acetabular liner (if used)
- o Compatible Stryker acetabular shell

Revision or removal of the Secur-Fit Advanced Hip Stem for device-related femoral fracture or aseptic loosening constitutes a failure. Revision or removal of the Secur-Fit Advanced Hip Stem for any reason requires study termination for the subject.

If revision of the femoral head or any acetabular component is required during the study, the event does not constitute a failure or study termination.

If the subject fails to return for his/her follow-up appointments, every effort should be made to contact the subject to assess his/her health status. If, after attempting to contact the subject through three documented phone calls and a certified letter, the subject still does not respond, he/she will be considered lost to follow-up. A Study Termination eCRF will be completed only after notifying Stryker of the subject's status and being given approval to terminate.

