12.3 Expected Complications and Rates of Occurrences

Complications associated with THA procedures, such as those performed with the Secur-Fit

Advanced Hip Stem, have been reported. These include the potential for: injury to the hip's

neurovascular structures, loosening of the components, malseating of the acetabular liner,

CONFIDENTIAL

heterotopic bone formation, infection, deep vein thrombosis, pulmonary embolism, metal sensitivity reactions, intraoperative or postoperative fracture of the femur or acetabulum, and the need for re-operation, revision, arthrodesis of the involved joint, girdlestone or amputation of the limb. The safety objective will compare the complication rates of the Secur-Fit Advanced Hip Stem to published rates.

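### Late operative-site complications are planned only as crude percentages with no time point and an undefined denominator, so they may be biased either way and do not match published fixed-time rates

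*Combined protocol and SAP*

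**What the plan says.** Section 9.2.2 gives the whole analysis of adverse events: "The frequency and percentage of all protocol-defined adverse events will be tabulated". It names no time point, censoring rule, person-time or confidence interval.

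The events it covers are defined in Section 8.1. One class is open-ended: "All AEs related to the operative site, regardless of seriousness or time of occurrence". The other, serious events between surgery and discharge, has a short fixed window. Section 3.4 sets the follow-up: "cases will be evaluated as per the evaluation schedule until each case reaches 10 years". Section 10.3 lists death, loss to follow-up, withdrawal and center termination as reasons for leaving, and adds: "Revision or removal of the Secur-Fit Advanced Hip Stem for any reason requires study termination for the subject".

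The denominator is in Section 9.4.4. The safety population is the *non-censored* subjects who received the stem, and the plan does not say what makes a subject censored.

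The percentages are meant for a comparison. Section 2.2 states: "It is expected that the AE rates reported for the Secur-Fit Advanced Hip Stem will be comparable to those reported in the literature". Section 12.3 states: "The safety objective will compare the complication rates of the Secur-Fit Advanced Hip Stem to published rates". Neither gives a time point.

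Some complications are handled with time in view. Section 9.2.1 counts revision/removal as a safety parameter, and Section 9.4.1 plans Kaplan-Meier curves for it, both all-cause and for aseptic loosening or device-related femoral fracture. Section 9.1.4 gives device-related femoral fracture a 30-day rate. Section 9.4.1 summarises the Follow-up Questionnaire by visit and lists the adverse events found through it.

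**The concern.** After those exceptions, what remains is late operative-site complications that do not end in stem revision: dislocation, infection, reoperation that spares the stem, unrevised loosening and the like. For these the plan offers one percentage with three things unsettled.

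- **Time.** Risk accumulates with follow-up, so an undated percentage has no published counterpart. Section 16 foresees publications at 2, 5 and 10 years, but 9.2.2 does not tie its table to them.
- **Attrition.** A subject who leaves early has less time in which to have an event. A crude percentage ignores this.
- **Denominator.** Whether a subject lost without an event stays in or drops out decides the direction of the error, and 9.4.4 leaves it open.

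At stake is the descriptive statement that complication rates are comparable with the literature. Without a time point, a clear denominator or an interval, a reader could neither check nor correct that statement.

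**Working it through.** **Inputs from the documents.** Loss to follow-up is in Section 9.4.2: "After factoring a 15% lost to follow-up rate, the final sample size is 326". Its time point is not stated; I read it as loss by year 5, when the primary endpoint falls. Cases: 314 (3.3). Enrollment: up to 24 months (3.4).

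**Assumptions.** True risk F of 5% (the documents give no complication risks); constant, independent hazards for event and loss; no deaths or stem revisions in the model; loss beyond year 5 continuing at the same pace; uniform entry.

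**The plan's own figure.** The safety analysis states none, but the sample size uses the 15%. For a one-sample test with p0 = 0.965, p1 = 0.99, one-sided 5% and 80% power:

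- n = (z_a·√(p0·q0) + z_b·√(p1·q1))² / 0.025² = 238.4
- with continuity correction, (n/4)·(1 + √(1 + 2/(0.025·n)))² = 276.99, so 277
- 277 / 0.85 = 325.9, so 326

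Both stated figures reproduce.

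**Attrition and denominator at 5 years, 15% loss.**

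- Event hazard: λ = −ln(0.95)/5 = 0.01026 per year
- Loss hazard: μ = −ln(0.85)/5 = 0.03250 per year
- Followed to year 5 without event: 0.95 × 0.85 = 0.8075
- Observed events per implanted case: λ/(λ+μ) × (1 − 0.8075) = 0.2399 × 0.1925 = 0.0462
- All implanted cases as denominator: **4.6%**, 8% too low in relative terms
- Only subjects with an event or complete follow-up: 0.0462 / (0.0462 + 0.8075) = **5.4%**, 8% too high

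**Other settings, true risk 5% throughout.**

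| Setting | All implanted | Events plus completers |
|---|---|---|
| 5 years, 15% loss | 4.6% (−8%) | 5.4% (+8%) |
| 10 years, 28% loss (1 − 0.85² = 0.2775) | 4.3% (−15%) | 5.9% (+17%) |
| 5 years, 15% loss, 80% of events before any loss | 4.9% (−1.5%) | 5.75% (+15%) |

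Early events shrink the first error and enlarge the second.

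**Pooled data cut.** If the table is cut when the last case reaches 5 years, entry over 24 months gives 5 to 7 years of follow-up. Over all implanted cases, a true five-year risk of 5% then shows as 6.0% without loss (+19%) and 5.4% with 15% loss per 5 years (+8%).

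**Time point.** At the same constant hazard, F(t) = 1 − 0.95^(t/5): 2.0% at 2 years, 5.0% at 5 years and 9.75% at 10 years. The choice of time point matters far more than attrition.

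**Precision.** Exact 95% intervals for 314 cases: 3 events (0.96%) gives 0.2% to 2.8%; 16 events (5.1%) gives 2.9% to 8.1%. None is planned for adverse events.

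**The case against.** Five points can be made for the plan.

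1. *Not all safety data are reported crudely.* This stands. A reader might infer from 9.2.2 that a count and percentage is the only safety analysis. The documents do not support that, given the Kaplan-Meier curves, the 30-day fracture rate and the perioperative window. The by-visit questionnaire summaries also bring in time, but they are not cumulative complication rates.
2. *The bias need not be downward.* This stands. A reader might infer that crude percentages understate risk. That requires all implanted cases as the denominator and a comparison at full follow-up. The wording in 9.4.4, or a pooled cut, can reverse the sign.
3. *Follow-up is equal by design.* True: 10 years is planned for every case. The inequality comes from attrition and from termination at stem revision.
4. *The effect is small.* On the plan's own 15% it is about 0.4 points on a 5% risk, well inside the sampling error. This limits the attrition point but not the missing time point.
5. *The comparison is descriptive, and publication at 2, 5 and 10 years supplies natural time points.* There is indeed no margin or decision rule, and no passage plans to set a 10-year percentage against a 2-year one. But publication dates are not analysis time points: without a rule, subjects with different lengths of follow-up enter the same table.

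**Conclusion.** The point holds for late operative-site complications other than stem revision/removal and 30-day device-related femoral fracture. For these the plan gives a crude percentage with no time point, censoring rule or interval and an undefined denominator, although it intends a comparison with published rates. The percentage may err either way: about 4.6% or 5.4% for a true five-year 5% at 15% loss, and about 4.3% or 5.9% for a true ten-year 5% at 28% loss. The documents do not support a claim that risk is understated, because they do not settle the denominator.

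These sizes rest on an assumed 5% risk, constant independent hazards, 15% read as loss by year 5, and completers plus events as one reading of *non-censored*. The lack of a time point rests on the text alone. This is a change that should be made; it does not touch the primary analysis.

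**What to change.** In 9.2.2:

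- Keep the crude table, based on all implanted cases and counting subjects with at least one event.
- For the main late operative-site complications (for example dislocation, infection and reoperation), add cumulative incidence from surgery at 2, 5 and 10 years with 95% confidence intervals. Censor at last contact. Treat death, and stem revision/removal when it is not itself the event, as competing events. Stem revision ends follow-up and can result from infection or fracture, so it should not be handled as independent censoring.
- Compare with literature only at matching time points, and say so in 2.2 and 12.3.

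In 9.4.4, remove *non-censored* from the safety population or define it.

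The cost is analysis wording and a little more programming. Onset dates are already reported (8.3) and termination dates already defined (10.3), so no new data are needed. Some reported rates may change slightly.
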